10.1.2 Serious adverse events

An SAE is defined as any adverse event [appearance of (or worsening of any pre-existing)] undesirable sign(s), symptom(s) or medical conditions(s)) which meets any one of the following criteria:

- fatal
- life-threatening
- life-threatening in the context of a SAE refers to a reaction in which the subject was at risk of death at the time of the reaction; it does not refer to a reaction that hypothetically might have caused death if it were more severe (please refer to the ICH-E2D Guidelines).
- results in persistent or significant disability/incapacity
- constitutes a congenital anomaly/birth defect
- requires inpatient hospitalization or prolongation of existing hospitalization, unless hospitalization is for:
 - Routine treatment or monitoring of the studied indication not associated with any deterioration in condition.
 - Elective or pre-planned treatment for a pre-existing condition that is unrelated to the indication under study and has not worsened since signing the information consent
 - social reasons and respite care in the absence of any deterioration in the subject's general condition
 - treatment on an emergency outpatient basis for an event not fulfilling any of the definitions of a SAE given above and not resulting in hospital admission
 - is medically significant, e.g. defined as an event that jeopardizes the subject or may require medical or surgical intervention to prevent one of the outcomes listed above

Medical and scientific judgment should be exercised in deciding whether other situations should be considered serious reactions, such as important medical events that might not be immediately life threatening or result in death or hospitalization but might jeopardize the subject or might require intervention to prevent one of the other outcomes listed above. Such events should be considered as "medically significant". Examples of such events are intensive treatment in an emergency room or at home for allergic bronchospasm, blood dyscrasias or convulsions that do not result in hospitalization or development of dependency or abuse (please refer to the ICH-E2D Guidelines).

All malignant neoplasms will be assessed as serious under "medically significant" if other seriousness criteria are not met and the malignant neoplasm is not a disease progression of the study indication.

Any suspected transmission via a medicinal product of an infectious agent is also considered a serious adverse reaction.

Advanced Accelerator Applications Clinical Trial Protocol (Version 01)

Confidential

10.1.3 Adverse Drug Reaction (ADR)

An ADR is any noxious and unintended response to an IMP related to any dose with at least a reasonably possible causal relationship with the IMP. Briefly, an ADR is an AE which is suspected to be possibly related to IMP by either the investigator or the study sponsor.

10.1.4 Suspected Unexpected Serious Adverse Reactions (SUSARs)

An ADR will be assessed to be "unexpected" if the nature, severity or frequency of the event is not consistent with the applicable product information available for the IMP. An ADR will be assessed to be "expected" if it is listed in the Investigator's Brochure.

A SUSAR is an adverse event regarded as serious with at least possible causal relationship to the drug, the nature, severity or frequency of which is not consistent with the applicable information available in the reference documents available for the IMP.

10.1.5 SAE reporting

To ensure subject safety, every SAE, regardless of causality, occurring after the subject has provided informed consent and until 2 days after the patient has stopped study treatment must be reported to AAA pharmacovigilance immediately without undue delay and under no circumstances later than 24 hours of learning of its occurrence. Detailed instructions regarding the submission process and requirements are to be found in the investigator folder provided to each site.

All follow-up information for the SAE including information on complications, progression of the initial SAE and recurrent episodes must be reported as follow-up to the original episode immediately without undue delay and under no circumstances later than 24 hours of the investigator receiving the follow-up information. An SAE occurring at a different time interval or otherwise considered completely unrelated to a previously reported one must be reported separately as a new event.

Information about all AE/SAEs is collected and recorded on the SAE report form; all applicable sections of the form must be completed in order to provide a clinically thorough report. The investigator must assess and record the relationship of each AE/SAE to each specific study treatment (if there is more than one study treatment), complete the SAE report form in English, and submit the completed form to AAA pharmacovigilance as per timelines defined above.

Follow-up information is submitted in the same way and timelines as the original AE/SAE Report. Each reoccurrence, complication, or progression of the original event should be reported as a follow-up to that event regardless of when it occurs. The follow-up information should describe whether the event has resolved or continues, if and how it was treated, and whether the patient continued or withdrew from study participation.

If the SAE is not previously documented in the Investigator's Brochure or Package Insert (new occurrence) and is thought to be related to the study treatment, AAA pharmacovigilance associate may urgently require further information from the investigator for health authority reporting. AAA may need to issue an Investigator Notification (IN) to inform all investigators involved in any study with the same study treatment that this SAE has been reported.

Advanced Accelerator Applications Clinical Trial Protocol (Version 01)

Confidential

Suspected Unexpected Serious Adverse Reactions (SUSARs) will be collected and reported to the competent authorities and relevant ethics committees in accordance with EU Guidance 2011/C 172/01 or as per national regulatory requirements in participating countries.

Any SAEs experienced after the 2-day period should only be reported to AAA Safety if the investigator suspects a causal relationship to study treatment.

10.1.6 Pregnancy reporting

To ensure subject safety, each pregnancy occurring after signing the informed consent form must be reported by the investigator to AAA Pharmacovigilance immediately without undue delay and under no circumstances later than within 24 hours of learning of its occurrence by using the Pregnancy form. The pregnancy should be followed up to determine outcome, including spontaneous or voluntary termination, details of the birth, and the presence or absence of any birth defects, congenital abnormalities, or maternal and/or newborn complications.

Pregnancy follow-up should be recorded on the same form and should include an assessment of the possible relationship to the study treatment and any pregnancy outcome. Any SAE experienced during pregnancy must be reported through the SAE report form.

10.1.7 Reporting of study treatment errors including misuse/abuse

All reports of intentional drug administration errors, misuse and abuse of the product are considered serious adverse event irrespective if a clinical event has occurred.

10.1.8 Annual Safety Report

For more information on AE and SAE definition and reporting requirements, please see the respective sections.

Once per year, the sponsor or PI will supply a report on the safety of trial patients with all available relevant information concerning patient safety during the reference period to the Competent Authorities of all Countries where the trial is being conducted. This report will also be supplied to the responsible ethics committee.

11 Data Collection and Database management

11.1 Data collection

The designated investigator staff will enter the data required by the protocol into the Electronic Case Report Forms (eCRF). The eCRFs have been built using fully validated secure web enabled software that conforms to 21 CFR Part 11 requirements. Investigator site staff will not be given access to the EDC system until they have been trained. Automatic validation programs check for data discrepancies in the eCRFs, allow modification and/or verification of the entered data by the investigator staff.

The Principal investigator is responsible for assuring that the data (recorded on eCRFs) is complete, accurate and that entry and updates are performed in a timely manner.

The Investigator must certify that the data entered are complete and accurate. After final database lock, the investigator will receive copies of the subject data for archiving at the investigational site.

All data should be recorded, handled and stored in a way that allows its accurate reporting, interpretation and verification.

11.2 Database management and quality control

Advanced Accelerator Applications personnel (or designated CRO) will review the data entered by investigational staff for completeness and accuracy. Electronic data queries stating the nature of the problem and requesting clarification will be created for discrepancies and missing values and sent to the investigational site via the EDC system. Designated investigator site staff is required to respond promptly to queries and to make any necessary changes to the data.

Concomitant treatments and prior medications entered into the database will be coded using the WHO Drug Reference List, which employs the Anatomical Therapeutic Chemical classification system. Medical history/current medical conditions and adverse events will be coded using the Medical dictionary for regulatory activities (MedDRA) terminology.

Data about all study treatment (s) dispensed to the subject and all dosage changes will be tracked on the study drug accountability logs. An electronic system for the Drug Supply Management might be implemented for this trial. The local monitor will provide training material to order the study drugs during the initiation visit. Once all the necessary actions have been completed and the database has been declared to be complete and accurate, it will be locked. Any changes to the database after that time can only be made after written agreement by Advanced Accelerator Applications.

After final database lock, the investigator will receive copies of the subject data for archiving at the investigational site.

11.3 Site monitoring

Before study initiation, at a site initiation visit or at an investigator's meeting, an Advanced Accelerator Applications representative will review the protocol and data capture requirements (eCRFs) with the investigators and their staff. During the study, Advanced Accelerator

Advanced Accelerator Applications Clinical Trial Protocol (Version 01)

Confidential

Applications employs several methods of ensuring protocol and GCP compliance and the quality/integrity of the sites' data. The field monitor will visit the site to check the completeness of subject records, the accuracy of data capture / data entry, the adherence to the protocol and to Good Clinical Practice, the progress of enrollment, and to ensure that study treatment is being stored, dispensed, and accounted for according to specifications. Key study personnel must be available to assist the field monitor during these visits. Continuous remote monitoring of each site's data may be performed by Advanced Accelerator Applications. Additionally, a central analytics organization may analyze data & identify risks & trends for site operational parameters, and provide reports to Advanced Accelerator Applications clinical teams to assist with trial oversight.

The investigator must maintain source documents for each subject in the study, consisting of case and visit notes (hospital or clinic medical records) containing demographic and medical information, laboratory data, electrocardiograms, and the results of any other tests or assessments. All information on eCRFs must be traceable to these source documents in the Subject's file. The investigator must also keep the original informed consent form signed by the subject (a signed copy is given to the subject).

The investigator must give the monitor access to all relevant source documents to confirm their consistency with the data capture and/or data entry. Advanced Accelerator Applications monitoring standards require full verification for the presence of informed consent, adherence to the inclusion/exclusion criteria, documentation of SAEs, and of data that will be used for all primary variables. Additional checks of the consistency of the source data with the eCRFs are performed according to the study-specific monitoring plan. No information in source documents about the identity of the subjects will be disclosed.

12 Data analysis and statistical methods

12.1 Analysis sets

The Safety Set (SAF) comprises all subjects who received any volume of the LysaKare[®] infusion in the study.

The Safety Set will be used for the analyses below, whereas the primary endpoint analysis is further restricted to an evaluable subset based on the following specification.

Potassium levels are evaluable for the primary endpoint only if there are at least 2 values measured from serum: one from baseline and one (minimum) from the post-treatment window where the acute serum potassium changes are expected. Therefore, the Primary Analysis Evaluable Set comprises of subjects who received any volume of the LysaKare[®] infusion and have both pre-dose and at least one post-dose (between 4 and 8 hours) potassium levels measured from serum.

12.2 Subject demographics and other baseline characteristics

Demographic and other baseline data including disease characteristics will be listed and summarized descriptively for the Safety set.

Categorical data will be presented as frequencies and percentages. For continuous data, mean, standard deviation, median, minimum, and maximum will be presented. For selected parameters, 25th and 75th percentiles will also be presented.

Relevant medical history and current medical conditions at baseline will be summarized separately by system organ class and preferred term.

12.3 Treatments

All subjects will receive an infusion of LysaKare[®] in the study, without co-administration of Lutathera[®].

12.4 Analysis of the primary endpoint(s)

12.4.1 Definition of primary endpoint(s)

The scientific objective guiding the primary analysis is to assess the effect of LysaKare[®] administration on serum potassium concentrations in GEP-NET patients eligible for Lutathera[®] treatment irrespective of treatment interruption or discontinuation. The primary endpoint is the change in serum potassium levels after LysaKare[®] IV administration compared to baseline.

The primary estimand is described by the following attributes:

- 1. The **target population** comprises patients diagnosed with SSTR positive GEP-NET and are eligible for treatment with Lutathera®.h
- The primary variable is change in serum potassium concentration from pre-dose to 2, 4, 6, 8, 12, and 24 hours after start of LysaKare® administration.

- 3. **Treatment of interest** is LysaKare® solution administered intravenously over a period of four hours.
- 4. **Intercurrent events** of interest in this study are treatment discontinuation for any reason and treatment interruption for any reason, which are ignored.
- 5. The **summary measure** is the mean of change in serum potassium levels from pre-dose to 2, 4, 6, 8, 12, and 24 hours, after beginning of LysaKare® administration.

12.4.2 Statistical model, hypothesis, and method of analysis

The study is descriptive in nature, and no hypothesis will be tested for study endpoints. The study will analyze and describe various primary variables related to potassium concentration, including mean change, maximum change, time to the maximum change, and the overall dynamics of the concentration curve during and after the LysaKare[®] infusion.

The primary endpoint analysis will be conducted on the Primary Analysis Evaluable Set.

In particular, maximum change and time to the maximum change will be summarized by descriptive statistics (N, median, minimum, maximum, and interquartile range). The mean (+/-SD) concentration-time profiles for serum potassium will be displayed graphically on the linear view.

12.4.3 Handling of missing values/censoring/discontinuations

There will be no replacement of missing data.

12.4.4 Sensitivity and Supportive analyses

Sensitivity analyses

The time course of the percent change as well as actual numerical change at each time point will be tabulated. A Mixed Model Repeated Measures will be fitted to assess the whole-time course.

12.5 Analysis of secondary endpoints

All other safety endpoints will constitute the secondary endpoints, see below.

12.5.1 Safety endpoints

Adverse events

All information obtained on adverse events will be displayed for the Safety set and by subject.

The number (and percentage) of subjects with treatment emergent adverse events (events started after the first dose of study medication or events present prior to start of treatment but increased in severity based on preferred term) will be summarized in the following ways:

- by primary system organ class and preferred term.
- by primary system organ class, preferred term and maximum severity.

• by Standardized MedDRA Query (SMQ) and preferred term

Separate summaries will be provided for study medication related adverse events, death, serious adverse events, other significant adverse events leading to discontinuation and adverse events leading to dose adjustment.

The number (and proportion) of subjects with adverse events of special interest/related to identified and potential risks (see Section 10.1) will be summarized.

A subject with multiple adverse events within a primary system organ class is only counted once towards the total of the primary system organ class.

Vital signs

All vital signs data will be listed by subject, and time and if ranges are available, abnormalities (and relevant orthostatic changes) will be flagged. Summary statistics will be provided by time.

12-lead ECG

PR, QRS, QT, QTcF, and RR intervals will be obtained from 12-lead ECGs for each subject during the study. ECG data will be read and interpreted locally. The ECG parameters will be summarized by time.

Clinical laboratory evaluations

All laboratory data will be listed by subject, and visit/time and if normal ranges are available abnormalities will be flagged. Summary statistics will be provided by treatment and time. Shift tables using the low/normal/high/ (low and high) classification will be used to compare baseline to the worst on-treatment value.

Grading of laboratory values will be assigned programmatically as per NCI Common Terminology Criteria for Adverse Events (CTCAE) version 5.0 or current version. The calculation of CTCAE grades will be based on the observed laboratory values only, clinical assessments will not be taken into account.

CTCAE Grade 0 will be assigned for all non-missing values not graded as 1 or higher. Grade 5 will not be used.

For laboratory tests where grades are not defined by CTCAE, results will be categorized as low/normal/high based on laboratory normal ranges.

12.6 Analysis of exploratory endpoints

Not applicable

12.7 Interim analyses

Not applicable

12.8 Sample size calculation

The primary endpoint is the change in serum potassium levels after LysaKare[®] IV administration compared to baseline. In a previous study, which assessed hourly potassium

Advanced Accelerator Applications Clinical Trial Protocol (Version 01)

Confidential

changes in 11 patients treated with LysaKare[®], peak concentration was observed at 2-4 h postbaseline, the mean baseline level was 4.2 mmol/L, mean increase at 2 h was 0.6 mmol/L and at 4 h it was 0.9 mmol/L (SD=0.3); the maximum increase was 1.5 mmol/L (Krenning 2000). The mild increase in potassium levels did not manifest in any safety issues or clinically significant events. Since the maximum mean increase was observed at 4h, the change from baseline to 4h will be of primary interest.

The current study will describe the expected mean change at 4h by a point estimate and the corresponding 95% confidence interval. In historical data a mean increase from baseline to 4h of 0.9 mmol/L was observed with a standard deviation of 0.3.

The criterion for choice of sample size will be based on length of confidence interval of the mean change at 4h calculated using the t-distribution. A requirement was initially chosen that the confidence interval has a total length not exceeding 0.2 mmol/L assuming the historical standard deviation to be valid, i.e. the distance should be no more than 0.1 mmol/L from the mean to the limit of the confidence interval when the estimated standard deviation is 0.3.

The initially estimated sample size of 38 subjects produces a two-sided 95% confidence interval with a distance from the mean to the limits that is equal to 0.099 when the estimated standard deviation is 0.3. With the required minimum number of 25 evaluable subjects for the primary endpoint analysis, the confidence interval (CI) total length is maintained with a slight increase to 0.25 mmol/L. Additionally, the originally estimated sample size of 38 implies an adequate probability of observing common AEs, see Table 12-1 below. This estimate holds true because the current laboratory sampling issue only impacts the evaluable number for the primary endpoint. Other safety assessments based on AEs remain evaluable for the whole safety set.

Sample size	Incidence of Adverse Event	
	5%	10%
10	0.401	0.651
20	0.642	0.878
30	0.785	0.958
38	0.858	0.982
40	0.871	0.985

Table 12-1 Likelihood of observing at least one case for given
sample size and incidence

The table displays the probability of observing at least one case of a certain AE which has the incidence 5% or 10% in this patient population for the sample sizes 10, 20, 30 and 40. Any further increase in total sample size ensures that this probability remains above 87%.

Since the sample size of 38 subjects assumes no drop-out, additional subjects have been added to hedge against drop-out. Given the design of the study, no or very minor drop-out is expected. The additional precaution is taken to ensure at least 25 subjects are evaluable for the primary endpoint analysis as discussed in the amendment rationale. Therefore, the adjusted sample size is approximately 45 subjects.

13 Ethical considerations and administrative procedures

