Confidential

	In order to calculate the sample size for the study, initially a requirement was chosen that the length of the 95% confidence interval of the mean change from baseline to 4h does not exceed 0.2 mmol/L at an observed historical standard deviation of 0.3. With a targeted minimum of 25 subjects evaluable for this endpoint, the length of this confidence interval is maintained with a slight increase to 0.25 mmol/L. The safety data analysis will be presented with special focus on LysaKare [®] related treatment emergent events and will be applied to the full Safety Set. Changes in Vital Signs and ECG will be summarized by time. Changes in laboratory parameters (Haematology and Blood Chemistry) will be described by time.
Key words	LysaKare [®] , amino acid, GEP-NET, PRRT, Lutathera [®]

Advanced Accelerator Applications Clinical Trial Protocol (Version 01)

Confidential

Version history

Version Number	Description
Global protocol v00 dated 12-Nov-2019	Initial global protocol. Approved in all countries.
Local protocol v00 PL.01 dated 18-May-2021	Local amended protocol from v00. Approved in Poland
Global protocol v01 dated 01-Dec-2022	Amended global protocol from v00 and local protocol v00-PL.01 dated 18-May-2021

Protocol Amendment 01

As of 08 November 2022, 30 patients were enrolled into the study and received an infusion of LysaKare[®].

Amendment rationale

The primary purpose of this amendment is to provide clarification on the sampling requirements for laboratory assessments. The Sponsor identified discrepancies in sampling used for electrolytes which were not performed as per protocol requested procedures. This resulted in samples collected with heparinized blood (2 patients) and whole blood (11 patients) instead of serum sampling across 4 sites. Therefore, the Visit Schedule and assessments in Section 8 have been updated to clarify the requirements of laboratory assessments.

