2.2 Analysis sets

Enrolled set

The enrolled set consists of all patients who signed informed consents and participated in the screening phase of the study.

Safety set

The safety set (SAF) comprises all patients who received any administration of the LysaKare[®] infusion in the study.

The safety set will be used for all analyses in this study, whereas the primary endpoint analysis is further restricted to an evaluable subset based on the following specification.

Evaluable set

Evaluable set comprises all patients who received any volume of the LysaKare® infusion and provided at least 2 potassium levels measured from serum: pre-dose value and at least one post-dose value from the post-treatment window where the acute serum potassium changes are expected (between 4 and 8 hours).

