2.5.2 Statistical hypothesis, model, and method of analysis

The study is descriptive in nature, and no hypothesis will be tested for study endpoints. The study will analyze and describe various parameters related to serum potassium concentration,

Advanced Accelerator Applications,	Confidential	Page 15 of 27
A Novartis company		
SAP amendment		CAAA001A12401

including mean change, maximum change, and time to the maximum change. In particular, maximum change and time to the maximum change will be summarized by descriptive statistics (N, median, minimum, maximum, and interquartile range).

The mean (+/- SD) concentration-time profiles for serum potassium concentration by treatment over time will be displayed graphically for the Evaluable set on the linear view.

To visualize the evolution of potassium level for each patient a spaghetti plot will be displayed along with a box plot to see the summary of potassium levels at each time point.

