2.13 Interim analysis

Not applicable.

3 Sample size calculation

The primary endpoint is the change in serum potassium levels after LysaKare® IV administration compared to baseline. In a previous study, which assessed hourly potassium changes in 11 patients treated with LysaKare®, peak concentration was observed at 2-4 h post-baseline, the mean baseline level was 4.2 mmol/L, mean increase at 2 h was 0.6 mmol/L and at 4 h it was 0.9 mmol/L (SD=0.3); the maximum increase was 1.5 mmol/L (Krenning et al., 2000). The mild increase in potassium levels did not manifest in any safety issues or clinically significant events. Since the maximum mean increase was observed at 4h, sample size calculations were based on the expected mean change in serum potassium levels at the 4h timepoint.

The current study will describe the expected mean change at 4h by a point estimate and the corresponding 95% confidence interval. In historical data a mean increase from baseline to 4h of 0.9 mmol/L was observed with a standard deviation of 0.3.

The criterion for choice of sample size will be based on length of confidence interval of the mean change at 4h calculated using the t-distribution. A requirement was initially chosen that the confidence interval has a total length not exceeding 0.2 mmol/L assuming the historical standard deviation to be valid, i.e. the distance should be no more than 0.1 mmol/L from the mean to the limit of the confidence interval when the estimated standard deviation is 0.3.

The initially estimated sample size of 38 subjects produces a two-sided 95% confidence interval with a distance from the mean to the limits that is equal to 0.099 when the estimated standard deviation is 0.3. With the required minimum number of 25 evaluable subjects for the primary endpoint analysis, the confidence interval total length is maintained with a slight increase to 0.25 mmol/L.

Additionally, the originally estimated sample size of 38 implies an adequate probability of observing common and very common AEs, see Table 3-1 below. This estimate holds true because the current laboratory sampling issue only impacts the evaluable number for the primary endpoint. Other safety assessments based on AEs remain evaluable for the whole safety set.

Advanced Accelerator Applications,	Confidential	Page 23 of 27
A Novartis company		
SAP amendment		CAAA001A12401

Table 3-1Likelihood of observing at least one case for given sample size and
incidence.

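### Does a minimum of 25 evaluable patients fail to deliver the stated 0.25 mmol/L confidence interval length at 4 h?

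*Protocol*

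**What the plan says.** Protocol 12.8 singles out one time point: "Since the maximum mean increase was observed at 4h, the change from baseline to 4h will be of primary interest". The initial requirement was a total interval length of no more than 0.2 mmol/L for the mean change at 4 h, from the t-distribution with a historical SD of 0.3. That led to 38 patients. After the sampling problem described in the rationale for Protocol Amendment 01, the section adds that with the required minimum of 25 evaluable patients "the confidence interval (CI) total length is maintained with a slight increase to 0.25 mmol/L". The synopsis ("the length of this confidence interval is maintained with a slight increase to 0.25 mmol/L") and SAP section 3 ("the confidence interval total length is maintained with a slight increase to 0.25 mmol/L") say the same.

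Protocol 12.1 defines the evaluable set as dosed patients who "have both pre-dose and at least one post-dose (between 4 and 8 hours) potassium levels measured from serum". SAP 2.2 has the same rule: "at least one post-dose value from the post-treatment window where the acute serum potassium changes are expected (between 4 and 8 hours". Protocol 12.4.3 says of missing values: "There will be no replacement of missing data". Protocol 9.1.2 allows a patient to be replaced only when no serum potassium was measured after the infusion.

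SAP 2.5.2 names the count explicitly only for two summaries: maximum change and "time to the maximum change will be summarized by descriptive statistics (N, median, minimum, maximum, and interquartile range".

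Protocol 4.1 says the sample size assumed a mean change below 1.1 mmol/L. That assumption does not appear in Protocol 12.8 or SAP section 3.

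**The concern.** The precision statement and the evaluability rule count different patients. Someone with serum values at 0 h and 6 h but none at 4 h counts towards the 25 and adds nothing to the 4 h mean. A missing 4 h value is not imputed and does not trigger replacement. The study tests no hypothesis, so the interval length is its only formal design criterion for the primary endpoint, and 25 is the smallest number whose unrounded length is at or below 0.25. The minimum could therefore be declared met while the 4 h interval is wider than advertised. Loss of usable potassium values has already happened here: 13 of the first 30 treated patients had non-serum samples.

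The wording adds to the doubt. A length said to be maintained would still satisfy the limit of 0.2, and 0.25 does not. The unused 1.1 mmol/L assumption suggests that two sample-size rationales are in circulation.

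**Working it through.** **Inputs.** SD 0.3, two-sided 95% t-interval, 38 initial patients and a minimum of 25 evaluable (Protocol 12.8). Enrolment of about 45 (Protocol 12.8). At the amendment, 30 patients had been treated, 2 + 11 = 13 of them with non-serum samples (amendment rationale). The documents give no rate of missing 4 h values, so the rates below are assumptions.

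**The plan's own figures.** Half-width = t(0.975, n−1) × 0.3 / √n, and length is twice that.

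- n = 38: 2.0262 × 0.3 / √38 = 0.0986, length 0.1972. The plan states 0.099. At n = 37 the length is 0.20005, just over the limit, so 38 is the correct minimum for 0.2.
- n = 25: 2.0639 × 0.3 / √25 = 0.1238, length 0.2477. The plan states 0.25.

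The arithmetic is right. The increase is 0.2477 / 0.1972 − 1 = 26%.

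**Fewer than 25 values at 4 h.**

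| Values at 4 h | CI length (mmol/L) |
|---|---|
| 25 | 0.248 |
| 24 | 0.253 |
| 23 | 0.259 |
| 22 | 0.266 |
| 20 | 0.281 |

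At the two decimals the plan uses, 24 values still give 0.25. Two must be missing before the figure becomes 0.26.

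**Chance of that with exactly 25 evaluable, misses independent.** P(at least two missing) = 1 − (1−p)^25 − 25p(1−p)^24. This is 2.6% at p = 1%, 8.9% at 2% and 36% at 5%. P(at least one missing) is 22%, 40% and 72%, but one missing value does not move the stated figure.

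**Chance at the planned enrolment.** If 45 are enrolled, all 13 affected patients are unusable and everyone else is evaluable, 45 − 13 = 32 remain. With all 32 values at 4 h the length is 0.216. Fewer than 25 would need at least 8 missing; the binomial probability is 0.014% at p = 5% and 1.2% at p = 10%.

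**Would requiring 25 values at 4 h secure 0.25?** No. The plan's figure holds when the estimated SD is 0.3, and the estimated SD varies. At n = 25 the length passes 0.25 once the observed SD exceeds 0.125 × √25 / 2.0639 = 0.303. With a true SD of 0.3 and normal data, that has probability P(χ²₂₄ > 24 × (0.3028/0.3)²) = 44%. With 24 values it is 50%. Sampling variation in the SD matters more than one absent value.

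**The case for a change.** The strongest case for acting is that 25 is the plan's declared floor, and a floor should deliver the property attached to it. Neither the enrolment buffer nor the mixed model in SAP 2.5.5, which uses patients without a 4 h value under a missing-at-random assumption, makes it do so. The repair would be cheap: tie the 25 to serum values at 0 h and 4 h, print the number beside the 4 h interval, and say that the criterion was relaxed.

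The mismatch stands as a description of the text. What does not follow is that a result would change.

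- The 0.25 is reported as a consequence of 25 patients at an SD of 0.3. The only upper limit the plan sets is the initial 0.2.
- Losing 4 h values alone should be uncommon. Patients remain in clinic until at least 12 h (Protocol 3.2), those who stop the infusion early continue assessments (Protocol 6.3.2), and SAP 2.1.1 keeps samples taken outside the time window.
- The sampling failure that cost 13 patients concerned the type of specimen. Those patients are excluded by the evaluability rule itself whenever they lack a serum value pre-dose or between 4 and 8 h.
- The evaluable set serves a primary variable with six time points (Protocol 12.4.1, SAP 1.2.1). Dropping a patient with 6 h and 8 h values because the 4 h value is absent would lose information elsewhere.
- Extending replacement to any missing 4 h value is a preference, directed at a shortfall that is improbable at the planned enrolment.

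**Conclusion.** No change follows. The sample-size figures are correct, and the analysis as planned gives a valid 4 h mean and 95% interval for however many 4 h values exist. Redefining the minimum would leave the estimate as it is and would not secure a length of 0.25. The realistic cost of the loose definition is an interval of 0.253 to 0.281 instead of 0.248 if one to five of exactly 25 values were missing. At about 32 evaluable patients the chance of having fewer than 25 values is 0.01% to 1.2% for missing rates of 5% to 10%. These probabilities rest on independent misses, on all 13 affected patients being unusable and on full enrolment of 45.

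The remaining points are clerical. The choice of verb is poor, but the limit of 0.2, the 38, the 25 and the 0.25 all stand in the same section, so the relaxation is in plain view. The 1.1 mmol/L sentence in Protocol 4.1 is a leftover: a mean change does not enter the formula for interval length, so it alters no figure. The number of patients contributing at each time point is something an analyst would print beside the mean and interval as a matter of course.
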